## eDiary OL Rimegepant Exposure

eDiary OL rimegepant exposure will be summarized descriptively by subgroup level and overall for all safety subgroups of interest described in Section 6.1.3.4, and will include the following parameters:

- Time on OL rimegepant (weeks)
- Number and percentage of subjects in the following time on OL rimegepant (weeks) categories:  $\geq 11$ ,  $\geq 23$ ,  $\geq 51$ . These correspond to using a 1-week lower bound on 3, 6, and 12 months, respectively.
- Cumulative OL rimegepant exposure (tablets)
- Average OL rimegepant exposure (tablets per month)
- Number and percentage of subjects in the subgroup categories defined in Section 6.1.3.4
- Number and percentage of subjects who took  $> 1$  OL rimegepant tablet on any 1 day
  - Single study drug record
  - Multiple study drug records
    - Subject-reported duplicate data
    - Subject-reported non-duplicate data
    - Both site-reported data on medication reconciliation form and subject-reported data
    - Site-reported data on medication reconciliation form only
- Total OL rimegepant exposure (tablets) summed across all subjects
- Total OL rimegepant exposure (patient-years), derived by summing (OL rimegepant end date – OL rimegepant start date + 1)/365.25 across all subjects.

### 6.2.6.2 Drug Accountability

Drug accountability is provided by the site on the Drug Accountability CRF.

#### Drug Accountability Exposure

Drug accountability exposure will be summarized with descriptive statistics by treatment group and overall for treated subjects:

- Time from first DB kit dispensed to last DB kit returned (weeks), derived as (latest DB kit return date – earliest DB kit dispense date + 1)/7. Subjects who were dispensed  $\geq 1$  DB kit but never returned any DB kit will be credited with 1 day.
  - Cumulative DB exposure (tablets) based on DB kits dispensed and returned, derived as summing (30 – number of tablets remaining) across records with non-missing DB kit dispense and return dates.
  - Average DB exposure (tablets per month) based on DB kits dispensed and returned, derived
-

as  $4 \times$  cumulative DB exposure based on DB kits dispensed and returned/time from first DB kit dispensed to last DB kit returned.

- Time from first OL kit dispensed to last OL kit returned (weeks), derived as (latest OL kit return date – earliest OL kit dispense date + 1)/7. Subjects who were dispensed  $\geq 1$  OL kit but never returned any OL kit will be credited with 1 day.
- Cumulative OL exposure (tablets) based on OL kits dispensed and returned, derived as summing (30 – number of tablets remaining) across records with non-missing OL kit dispense and return dates.
- Average OL exposure (tablets per month) based on OL kits dispensed and returned, derived as  $4 \times$  cumulative OL exposure based on OL kits dispensed and returned/time from first OL kit dispensed to last OL kit returned.
- Time from first DB or OL rimegepant kit dispensed to last DB or OL rimegepant kit returned (weeks). This is time from first DB kit dispensed to last DB kit returned for subjects whose as-treated treatment group is rimegepant. This is time from first OL kit dispensed to last OL kit returned for subjects whose as-treated treatment group is placebo.
- Cumulative DB or OL rimegepant exposure (tablets) based on DB or OL rimegepant kits dispensed and returned. This is cumulative DB and OL combined exposure for subjects whose as-treated treatment group is rimegepant, and cumulative OL exposure for subjects whose as-treated treatment group is placebo.
- Average DB or OL rimegepant exposure (tablets per month) based on DB or OL rimegepant kits dispensed and returned, derived as  $4 \times$  cumulative DB or OL rimegepant exposure based on DB or OL rimegepant kits dispensed and returned/time from first DB or OL rimegepant kit dispensed to last DB or OL rimegepant kit returned.

eDiary versus drug accountability cumulative exposure will be summarized by treatment group and overall with the number and percentage of subjects in the following categories:

- $\geq 10$ ,  $\geq 20$ ,  $\geq 30$  absolute tablet difference in cumulative DB exposure for treated subjects
- $\geq 10$ ,  $\geq 20$ ,  $\geq 30$ ,  $\geq 40$ ,  $\geq 50$  absolute tablet difference in OL rimegepant exposure for OL rimegepant treated subjects.

Absolute tablet difference is defined as the absolute value of {eDiary cumulative exposure (tablets) – drug accountability cumulative exposure (tablets)}.

### **Drug Accountability Compliance**

Drug accountability compliance will be summarized by as-randomized treatment group and overall with the number and percentage of randomized subjects in the following categories:

- Any kit dispensed
- Did not return  $\geq 1$  kit dispensed and discontinued study drug, defined as any of the following:
  - Randomized subjects who were not treated and did not return  $\geq 1$  DB kit dispensed

- Treated subjects who did not return  $\geq 1$  DB kit dispensed and discontinued DBT (i.e., non-missing DBT last date)
- OL rimegepant treated subjects who did not return  $\geq 1$  OL rimegepant kit dispensed and discontinued OL rimegepant (i.e., non-missing OL rimegepant last date).
- Did not return any kit dispensed and discontinued study drug.

Kit dispensed and kit returned will be identified from “yes” responses to the questions “was this kit dispensed” and “was this kit returned”, respectively.

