[REDACTED]							[REDACTED]
[REDACTED]							[REDACTED]
[REDACTED]							[REDACTED]
Migraine Disability Assessment (MIDAS)				X			X (week 12 only)

¹ Concomitant medications, including prophylactic and standard of care migraine medications, taken during Observation Period and rescue medication taken during the Treatment Phase should be recorded in the subject's paper diary and reviewed by study personnel at each visit. Female subjects will also record menstrual period information on the paper diary which should be reviewed by study personnel at each visit.

² The actual baseline visit date should be used for IWRS enrollment date and eligibility date.

³ Height measured at Screening Visit only. Weight, body temperature, respiratory rate, blood pressure, and heart rate will be collected at all timepoints where indicated. Sitting arterial systolic and diastolic blood pressure and radial artery pulse rate will be measured.

⁴ SAEs, AEs, and Concomitant Procedures must be reported after subject signs informed consent. SAEs should be reported from signing of consent through the 8-week Follow up Safety Visit. Non-serious AEs should be reported from signing of consent through 2-Week Follow up Safety Visit.

⁵ Subjects should finish a bottle of study medication before starting a new bottle. Study drug will be dispensed at monthly (every 4 weeks) study visits, as needed. Unscheduled visits to dispense study medication may be scheduled as needed. At the Week 12 Visit, the open-label study medication will be dispensed and subjects will be instructed not to begin taking rimegepant until confirmation from site staff pending lab results.

⁶ Subjects must take their study medication every other day, regardless of whether or not they have a migraine. Subjects must report each tablet they take in the eDiary. Doses are not required to be taken in the office on days of a study visit, however dosing requirements and compliance should be discussed with subjects at all visits.

⁷ The Observation Period to determine eligibility is 28 days +3 days. The “+3” days window is included for scheduling purposes only. Subjects with less than 24 completed eDiary reports during the Observation Period will not be considered for participation due to non-compliance with the eDiary. Subjects in the Double-blind, Treatment phase who demonstrate poor compliance will be discussed with the Sponsor and corrective training will be completed by the site with the subject.

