4.3.3 Open-label Extension Phase (52 weeks)

It is estimated that approximately 675 subjects will be entered into the open-label extension phase.

As indicated in Table 1, laboratory tests will be performed at the Week 12 visit (final visit of the double-blind treatment phase of the study). Subjects who continue to meet all inclusion/exclusion criteria and have been compliant with the eDiary may enter the open-label extension phase, pending review of laboratory test results. Subjects will be dispensed study medication and will be instructed that they cannot take study medication until laboratory results

confirm study eligibility. Subjects may be contacted by telephone; an office study visit is not required.

Subjects will be instructed that they must take one tablet of study drug every other calendar day, regardless of whether they have a migraine on that day or not. If subjects in this group have a migraine on a day that they are not scheduled to dose with study medication, they may take 1 study medication tablet on that calendar day to treat a migraine. Therefore, if needed, subjects can take a maximum of one tablet of study medication per calendar day for 52 weeks during the Open-label, Extension Phase.

The electronic subject diary will be completed by subjects to capture dosing of study medication and the frequency and severity of migraines during the Open-label, Extension Phase.

Subjects will also use the eDiary to complete [REDACTED] and [REDACTED]. The Migraine-Specific Quality-of-Life Questionnaire v 2.1 (MSQ), the Sheehan Suicidality Tracking Scale (S-STSS), Migraine Assessment Disability (MIDAS) and [REDACTED] will be completed, or administered by the investigator, on paper at specified study visits (Table 2).

Study visits will be approximately every two weeks during the first month and then every 4 weeks, until Week 64 (Table 2). At each visit, the eDiary will be reviewed by site staff for completeness and compliance. Study medication compliance and concomitant medication use and menstrual period information (female subjects) will be reviewed (and compared to the eDiary and paper diary entries, where applicable) and subjects will be dispensed additional study medication as needed. Additional safety (including laboratory tests and ECGs) will be performed per the schedule outlined in Table 2.

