7.4 Treatment Compliance

Responsible study personnel will dispense the study drug. Subjects should finish a bottle of study medication before starting a new bottle. Accountability and compliance verification should be documented in the subject's study records.

Subjects must be counseled on the importance of taking the study drug as directed (see Section 7.2.2). Treatment compliance, review of study medication doses reported in the eDiary and through review of returned study medication, should be assessed by site staff at each study visit. Discrepancies between doses reported in the eDiary, review of study medication and information provided by subject must be documented in the source record. Incorrect or missing dosing data and migraine data that are reported in the eDiary will be corrected through either a

Data Clarification Record or a Medication Reconciliation Form. Investigators should inform Subjects that involuntary termination from the study will occur in cases where non-compliance is identified. Study staff should contact a subject in between the monthly study visits if the subject demonstrates non-compliance with the eDiary and document the contact in the source, to identify potential lost to follow up subjects as early as possible.

Investigators must monitor subjects for possible cases of abuse of study medication (subjects taking study drug for non-therapeutic purposes, e.g. for psychoactive effects such as high or euphoria). Investigators should also assess study drug accountability discrepancies (e.g. missing study medication, loss of drug, or non-compliance cases in which more study medication was used, as compared to expected). Investigators should obtain more information and explanation from subjects when there are study drug accountability discrepancies. See Section 8.1.1.

Cases of potential study medication abuse or overdose (including cases of non-compliance with study medication dosing instructions or subjects who discontinue treatment without returning study medication) should be documented in the source record and reported as an AE or SAE as appropriate. Dosing errors (e.g. accidentally taking 2 tablets in one calendar day) should be reported as deviations.

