- **OL rimegepant treated subjects:** Enrolled subjects who received at least one dose of OL rimegepant, i.e., non-missing OL rimegepant start date.
  - **Interim subjects:** OL rimegepant treated subjects with OL rimegepant start date – DBT last date  $> 7$  days.
- **DB or OL rimegepant treated subjects:** Enrolled subjects who received at least one dose of rimegepant (DB or OL) i.e., non-missing DB or OL rimegepant start date. This corresponds to the Rimegepant Safety Analysis Set in the BHV3000-305 Protocol.
- **Follow-up subjects:** Treated subjects whose last contact date is in the follow-up safety analysis period.
- **Coronavirus Disease 2019 (COVID-19) impacted:** Enrolled subjects who are impacted by COVID-19 (see Section 9.1.2).

See Sections 7.3 and 7.4 for derived dates and analysis periods, respectively.

---

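### The kit-return table counts an unreturned open-label bottle only for subjects who recorded an open-label dose, so a bottle handed out at Week 12, never started and kept is not tabulated as unreturned

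*SAP*

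**What the plan says.** The compliance table in SAP 6.2.6.2 is presented by randomized group "with the number and percentage of randomized subjects in the following categories". One row is for subjects who stopped study drug with one or more dispensed kits outstanding. It is met by any of three cases:

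- Case 1 begins "Randomized subjects who were not treated and did not return" and concerns DB kits.
- Case 2 begins "Treated subjects who did not return", concerns DB kits, and requires a DB treatment last date.
- Case 3 begins "OL rimegepant treated subjects who did not return", concerns OL kits, and requires an OL last date.

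SAP section 3 defines the group named in case 3 as "Enrolled subjects who received at least one dose of OL rimegepant, i.e., non-missing OL rimegepant start date". A further row counts subjects who stopped and returned no kit at all.

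On supply, footnote 5 to Protocol Table 1 says: "At the Week 12 Visit, the open-label study medication will be dispensed and subjects will be instructed not to begin taking rimegepant until confirmation". The go-ahead is given by the site once the Week 12 laboratory report is in. Protocol 4.3.3 repeats the point: subjects are "instructed that they cannot take study medication until laboratory results" show them to be eligible, and that contact may be made by telephone. A bottle holds 30 tablets (Protocol 7.2.2).

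**The concern.** Dispensing comes before clearance, so a subject can hold a bottle of active drug without ever joining the OL treated group. Case 1 shows that the row is meant to include people who were given a kit and never dosed from it. The DB version of that situation is covered and the OL version is not.

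The SAP knows this group elsewhere. SAP 6.2.3.3 tabulates subjects who completed the double-blind phase without going on to open label. SAP 7.3 gives a study drug last date, even at an interim lock, to subjects with DB completion status who are not continuing and have no OL start date. They fit the row's title, having stopped with a kit outstanding, and drop out only through its sub-definition.

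Protocol 7.4 includes "subjects who discontinue treatment without returning study medication" among cases of potential abuse or overdose to be documented and reported. A kit-return row that omits some of these subjects understates what it is labelled to show.

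**Working it through.** The SAP states no figure for this row, so there is nothing to reproduce. The check applies the rule as written to each kind of subject.

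**Setting.** The subject was treated in the double-blind phase, was given an OL bottle at Week 12, did not return it, and has the relevant last dates. Case 1 cannot apply because the subject was treated. Case 2 applies if any DB kit is outstanding. Case 3 applies only if an OL dose is recorded.

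| OL dose recorded | DB kits outstanding | Row: at least one kit not returned | Through the OL case | Row: no kit returned |
|---|---|---|---|---|
| No | None | **No** | No | **No** |
| No | Some | Yes | No | No |
| No | All | Yes | No | Yes |
| Yes | None | Yes | Yes | No |
| Yes | Some | Yes | Yes | No |
| Yes | All | Yes | Yes | Yes |

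The first line is the gap. The OL bottle is outstanding in all six lines, and only the first is missed by both rows. Recording one OL dose, with all else equal, turns that line into the fourth, which is counted.

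**What counts as an OL dose.** SAP 7.3 labels any study drug record on or after the Week 12 kit assignment as open label, whichever bottle the tablet came from. A subject who records even a leftover DB tablet after assignment is therefore classed as OL treated and is counted. The missed group is limited to subjects with no study drug record from that point.

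**Other accountability output.**

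- The tablet-difference rows for OL exposure in SAP 6.2.6.2 are restricted to OL treated subjects, so they give no substitute count.
- The exposure summary in the same section covers all treated subjects. It credits 1 day to anyone given an OL kit who never returned one, so the missed subjects do enter that table, as a duration.
- The by-subject exposure and accountability listing in SAP 6.2.6.1 covers all randomized subjects and all accountability data.

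**Size.** Protocol 5.1 plans about 800 randomized and about 675 entering open label.

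- Planning ceiling, reading entry as taking an OL dose: 800 − 675 = 125, and 125/800 = 15.6%. This includes subjects who left before Week 12 and never had an OL bottle, so the true number is lower.
- Illustration A (assumed): 10% to 50% of the 125 hold a bottle and 5% to 20% of those keep it. 125 × 0.10 × 0.05 = 0.6 and 125 × 0.50 × 0.20 = 12.5 subjects, or 0.08% to 1.6% of 800.
- Illustration B (assumed): 5 to 50 holders who never start, of whom 10% to 100% keep the bottle. 5 × 0.10 = 0.5 and 50 × 1.00 = 50 subjects, or 0.06% to 6.3% of 800.

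Neither set of proportions comes from the documents. Both ranges start below one subject.

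**The case against.** The best defence is that this is one descriptive row, that the raw kit data are listed, and that return is already controlled. Subjects who do not enter open label should attend the end-of-treatment and follow-up visits and must return unused medication (Protocol 4.3.4). Sites must also log amounts dispensed, returned and lost (Protocol 10.5). All of that stands. It limits the importance of the point but does not make the row agree with its title.

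A reader might infer more than the text supports:

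- *That these bottles appear in no table.* They enter the exposure summary at 1 day. A holder can also reach the compliance table through an unreturned DB kit or through the row for no kit returned.
- *That this is the only tabulation of potential abuse.* It is the kit-return tabulation. SAP 6.5.1.2 and 6.5.1.4 separately tabulate potential drug abuse adverse events. Whether a kept bottle would be reported as one depends on the site and perhaps on definitions in the BHV3000 Core SAP, which is not among the documents reviewed.
- *That any use by these subjects falls outside the rimegepant safety set.* That set requires one rimegepant dose, double-blind or open-label. Subjects treated with double-blind rimegepant are already in it. Only unrecorded use by placebo subjects would fall outside.
- *That many subjects are affected.* The documents give neither the number who never start nor the share who keep the bottle.

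**Conclusion.** Wrong as written, minor. The row omits a treated subject who returned all DB kits, has no study drug record on or after the Week 12 kit assignment, does not continue to the extension and keeps the OL bottle. That subject is a non-returner in no kit-return row, although the matching DB case is covered. What is lost is a tabulated count, not the data.

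The conclusion about the rule follows from the definitions alone. The size does not: the planning ceiling is 125, the true number is probably far smaller, and it may be zero. No endpoint, estimand, power figure, type I error or safety-set membership depends on the row.

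**What to change.** Keep the three cases and add a fourth: treated subjects with at least one OL rimegepant kit dispensed, at least one OL kit not returned, and a missing OL rimegepant start date. Before final database lock, also require a no response to continuing to OL on the DB Subject Status CRF. At final lock, include all such subjects. Show the fourth case as a sub-row.

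The condition before final lock is needed. SAP section 4 times the Week 12 analysis to the last treated subject's last double-blind visit, when some subjects may hold a new OL bottle and still be awaiting laboratory clearance. Without the condition they would be counted as non-returners.

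The cost is one SAP line and one table re-run from Drug Accountability and Subject Status data already collected. The reported non-return count may rise slightly.

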### 6.2.6.3 *eDiary Compliance*

#### **eDiary Compliance During Pre-Randomization and in the DBT Phase**

eDiary compliance in the OP and DBT phase will be summarized descriptively by treatment group and overall for treated subjects for each source (subject; subject or site). Subject sources are the scheduled dosing report, evening report headache log, follow-up headache log, PoM, and SM survey. Site source is the medication reconciliation form.

Finding days are those with complete finding dates from any subcategory of question. Compliance will be derived for the following periods:

- Last 28 days before randomization:  $100 \times (\text{total number of finding days in the last 28 days before the IWRS randomization date})/28$
- Randomization to last DBT visit:  $100 \times (\text{total number of finding days from the IWRS randomization date to the last DBT visit date})/(\text{total number of days from the IWRS randomization date to the last DBT visit date})$ .

DBT start date will be used if IWRS randomization date is missing.

For each source and period, eDiary compliance will be summarized as a continuous parameter and as the number and percentage of subjects with  $\geq 80\%$  and  $\geq 90\%$  compliance.

#### **eDiary Compliance in the DB or OL Rimegepant Phase**

eDiary compliance in the DB or OL rimegepant phase will be summarized analogously to eDiary compliance by treatment group and overall for DB or OL rimegepant treated subjects.

Compliance will be derived for the following period:

- DB or OL rimegepant start to last DB or OL rimegepant visit:  $100 \times (\text{total number of finding days from the DB or OL rimegepant start date to the last DB or OL rimegepant visit date})/\text{total number of days from the DB or OL rimegepant start date to the last DB or OL rimegepant visit date}$ .

#### 6.2.6.4 *Non-Study Medications*

Non-study medications will be summarized by therapeutic class and preferred name. For each subject, multiple records of the same medication will be counted only once within each therapeutic class and preferred name. Medications will be displayed in descending order of overall frequency within therapeutic class and preferred name, unless specified otherwise.

Non-study medications will be identified from the Concomitant Medication and Migraine Standard of Care Medications CRFs.

Migraine standard of care medications are defined as those reported on either the (1) Migraine Standard of Care Medications CRF, or (2) Concomitant Medication CRF with medical history, AE, additional AE, or other indication indicative of migraine.

Prophylactic migraine standard of care medications are defined as migraine standard of care medications with a “yes” response to the question about prophylactic migraine medication on the Migraine Standard of Care Medications CRF. Otherwise, all other migraine standard of care medications will be considered to be non-prophylactic.

See Section 7.6.3 for the definitions of non-study medication types, e.g., prior, current, DBT concomitant, DB or OL rimegepant concomitant, follow-up.

By-subject listings of non-study medications and standard of care migraine medications will be provided by therapeutic class and preferred name for enrolled subjects, and will display COVID-19 visit impact code for visits impacted by COVID-19 (see Section 9.1.5.2). Prophylactic and non-prophylactic migraine standard of care medications will be identified, as well as medication type.

Refer to the BHV3000 Core SAP for non-study medication start and stop date imputation, and listing content.

